Infants with intestinal failure require chronic administration of parenteral nutrition (TPN). The population under one year of age on TPN is at greatest risk for parenteral nutrition associated cholestasis (PNAC), but, even among older individuals on TPN, the emergence of cholestasis carries a bad prognosis. A number of factors play a role in PNAC. These include endotoxemia, prolonged fasting, immaturity of bile secretory mechanisms among infants, intravenous infusion of high glucose concentrations, intravenous infusion of high protein loads, and intravenous infusions of soy based lipid emulsions. Human data reveal that TPN administered to infants for over three weeks is associated with PNAC. Further analysis reveals that cholestasis is closely associated with the administration of soy-based lipids which contain potentially hepatotoxic phytosterols. Thus lipid reduction strategies have been employed for reversal of PNAC. They sometimes work, but put infants at risk for essential fatty acid deficiency. An alternative strategy of providing lipid in the form of Omegaven®, a fish oil-derived emulsion, is extremely promising, and has been used successfully with virtually no complications in an uncontrolled trial at Boston Children's Hospital. Ongoing controlled studies of Omegaven® are underway at Boston Children's Hospital, and several other institutions have published small case series or case reports suggesting that Omegaven® is effective and safe. It is not FDA approved because none of the ongoing placebo controlled trials have been completed yet in the United States, but, because of its anti-inflammatory properties, it is approved in several European countries for use in adults with inflammatory conditions. Every year, we observe several children in our own practice who have no hope of coming off TPN for several months and who have progressive cholestasis. Our own unpublished data suggest that once PNAC has been established in the absence of endotoxemia, it is usually reversible. However, this may not be true if less than approximately 70% of daily calories are derived enterally. We also have published data in abstract form suggesting that a high conjugated bilirubin to gamma GT ratio is a poor prognostic sign. This study provides Omegaven® for compassionate release to those infants within our practice who have developed progressive cholestasis despite reduction in parenteral lipid below one gram per kilogram

body weight per day, and who are unlikely to tolerate substantial enteral nutrition until several months following their small intestinal insult.

II. Purpose of Study

The specific aim of this study is to ascertain whether PNAC can be reversed if a fish oil-based intravenous lipid product (Omegaven®) at a dose of up to 1 g/kg body weight/day is substituted for a soy-based intravenous lipid product (Liposyn® or Intralipid®) as part of the daily TPN of infants and children with intestinal failure and PNAC. Secondary aims will be to confirm the safety of Omegaven®.

III. Background

In North America, infants and children who require parenteral nutrition (TPN) customarily receive solutions whose caloric distribution is balanced between glucose, protein, and fat to provide approximately 60-70 % of calories via glucose, 10-15 % of calories via protein, and 20-30% of calories via lipid.(1) Commercial lipid solutions utilized in North America are customarily soy-based, and contain high quantities of phytosterols including sitosterol and stigmasterol. Animal data suggest that high quantities of stigmasterol inhibit fxr, a nuclear receptor in the hepatocyte that helps to regulate bile acid homeostasis by controlling expression of bile acid export pumps. (2) Thus, exposure to a high quantity of stigmasterol is potentially hepatotoxic to individuals who have a propensity for cholestasis due to a poorly developed bile secretory process.

It is known that infants and children with underlying intestinal failure are at extraordinarily high risk for cholestasis. (3) The cholestatic process is reversible in approximately ¼ of infants with parenteral nutrition associated cholestasis (PNAC), even when soy-based lipid emulsions are given parenterally, if those infants can experience small intestinal adaptation and ultimately tolerate and assimilate the majority of their calories via enteral nutrition. Unfortunately, if adaptation does not occur rapidly enough, PNAC may progress to endstage liver disease resulting in death or necessitating combined liver/small intestinal transplantation.

A popular strategy for minimizing the toxicity of lipid emulsions is to reduce the amount of lipid in parenteral nutrition to between 0.5 g/kg body weight/day and 1g/kg body weight/day. (4) Preliminary results suggest that this strategy is beneficial for some infants, but that it is not universally effective. One potential reason for lack of effectiveness among some cholestatic infants is that endotoxemia is commonplace in children with intestinal failure receiving TPN, and that stigmasterol potentiates the cholestatic effect of endotoxin upon the liver. Therefore, when the infant with a cholestatic propensity is exposed to endotoxin and even modest quantities of stigmasterol, cholestasis could progress.

An alternative liver-protective strategy for children on TPN has been to provide all of the patients' parenteral lipid in the form of a fish-oil based product called Omegaven®. (5) This product has been used for over 10 years as an adjunct to conventional fat emulsions.

According to current data, an increase in the proportion of omega-3 fatty acids is thought to optimize nutrition in general, but in particular benefit patients whose underlying disease might benefit from an increase in omega-3 fatty acids. An adequate intake of omega-3 fatty acids results in anti-inflammatory and immunomodulatory effects that are protective against inflammatory tissue damage and capillary permeability. In addition, adults on Omegaven® seem to display improved immunological resistance. Omegaven® may also reduce the risk of thrombosis and increase microvascular perfusion due to its anti-aggregatory and vasodilatory effects.

In Europe and Asia, parenteral omega-3 fatty acids have been used in the following adult patient populations:

1. post traumatic and post surgical patients
2. patients experiencing early stages of sepsis/SIRS
3. patients at risk of hyperinflammatory processes
4. patients with inflammatory bowel disease (Crohn's disease, ulcerative colitis)
5. patients with inflammatory skin diseases (psoriasis, atopic eczema)

The dosing used in these patients was 0.1 (1ml) to a maximum of 0.2 g (2ml) /kg body weight. The infusion rate used did not exceed 0.5ml/kg/body weight/hour. Since it was intended to be infused in combination with conventional fat emulsions, the total fat intake was limited to 10-20% as fish oil. The duration of administration did not exceed 4 weeks.

Two non-North American trials suggest that Omegaven® is safe when administered to young children. (6,7) These trials were performed in Germany and Taiwan. The German study was a controlled, randomized, open parallel-group clinical study to investigate whether or not omega-3 fatty acids could be incorporated into the plasma phospholipids of very low birth weight preterm infants. In this 7-day safety trial, Omegaven® use was evaluated on the basis of clinical, laboratory, and antioxidant parameters and lipid metabolism. Treatment was started on day 3-5 of life and continued for a total of 7 days. Patients received Omegaven® plus conventional soybean fat emulsion or soybean emulsion alone. The maximum dose of Omegaven® in the study was 0.2 gm/kg/day. The study concluded that the Omegaven® was well tolerated in this group of preterm infants in respect to both hematological and biochemical parameters. The incidence of reported adverse events between both study groups was similar. The eicosapentaenoic acid (EPA) content of plasma phospholipids increased significantly in the Omegaven® arm, with the proportion of EPA to the total fatty acids reaching almost three times the baseline value. The sum of omega-3 fatty acids showed a significantly greater increase in the Omegaven® group compared to the conventional treatment arm.

The Taiwanese study was a single center, controlled, open-labeled study conducted to investigate the safety of parenteral administration of Omegaven® in preterm infants. The group of 20 infants were randomized to one of two treatment groups; one consisting of Omegaven®/conventional lipids and the other consisting of conventional lipids alone. The average dose of Omegaven® in the treatment group of this 14-day study was 0.13 ± 0.02 g/kg/day. There were no significant differences between the two groups with regard

to body weight and length. Similarly, there was no significant difference in the hematological or biochemical parameters. There were no adverse events that were attributable to Omegaven® use. It was concluded that Omegaven® was well tolerated in these preterm infants.

While non-North American studies conclude that Omegaven® is safe and that it may have anti-inflammatory properties, they do not address a potential liver protective effect for the agent. Data from North America suggest a salutary role for Omegaven® in PNAC. The group at Boston Children's hospital had initially utilized Omegaven® in a child with soy allergy who required TPN. (8) Subsequently, they reported upon two children who received Omegaven® for PNAC, demonstrating that cholestasis resolved in both and that neither of them experienced side effects. (9). A subsequent open label trial performed at Boston Children's Hospital showed both safety and resolution of cholestasis in 18 children with advanced PNAC.(5) Historical controls receiving soy-based lipid emulsions showed progression of cholestasis rather than resolution. Currently, a double blind, controlled study comparing 1 g/kg body weight/day of Omegaven® with 1 g/kg body weight/day of Intralipid® is being conducted in Boston, and results are quite promising ([name], personal communication). Many other pediatric institutions, including our own, have utilized Omegaven® to treat PNAC. This agent is available in over 30 institutions, and no significant adverse effects have been reported. Small case series and case reports have been published confirming safety and suggesting effectiveness for PNAC (10).

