5. Lack of appetite, nausea, vomiting
6. Dyspnea
7. Headache, pain in the chest, bone pain
8. Priapism
9. Increase/decrease blood pressure
10. Anaphylactic reactions/erythema

Risks for blood draw:

- Occurrence of discomfort and/or a bruise at the site of puncture
- Less commonly, fainting
- The formation of a clot or swelling in the vein and surrounding tissue
- Bleeding from the puncture site
- On rare occasions an infection may develop at the site where the blood is collected

Potential Risks of No Treatment

Since Omegaven® will only be offered to those patients for whom no standard therapy has been safe and effective, the risks of not being treated are those allowing for the natural history of their disease and associated clinical manifestations to progress. These include fulminate liver failure and death.

VII. Overall Risk Assessment

Patients will be at some risk inherent in taking a pharmaceutical agent that has not been fully evaluated for long duration treatment. However, the availability of safety data demonstrates no life-threatening risks or toxicities to vital organs or physiologic functions. The potential benefits of Omegaven® in this patient population are mainly based on human trials and our own experience.

VIII. Risk Category

The research involves greater than minimal risk, but presents the prospect of direct benefit to the individual subjects.

IX. Methods

A. Subject Selection

No concomitant medications will prohibit enrollment.

Inclusion Criteria

1. Males and females ages one month of age to 18 years of age
2. Patients with intestinal failure on TPN
3. Patients who have a conjugated or direct bilirubin of ≥ 3 mg/dl for more than 4 weeks and in whom other causes of cholestasis have been excluded with reasonable certainty utilizing biochemical, serologic, microbiologic, and radiographic techniques. Liver biopsy is not required to rule out other disorders, but may be utilized at the clinician's discretion
4. Patients in whom reduction of IV soy-based lipid load to an **average** <1.2 g/kg body weight/day has failed to reduce the conjugated or direct bilirubin within ≥ 30 days of implementation

5. Willing to use birth control during study participation for females of child-bearing potential, as determined by investigator.
6. Signed informed consent for use of Omegaven® obtained

Exclusion Criteria

1. Any of the contraindications to use of Omegaven®

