Following completion of the study medication, subjects will be seen for a final study visit within 1 month for a follow-up assessment. A complete, comprehensive history and physical will be performed. Blood samples will be collected and a urine pregnancy test will be done for females of childbearing potential. Adverse events and concomitant medications will be documented by the study staff.

The following table summarizes Study Procedures:

Study Procedures Table

	Baseline (Day 0)	Weekly while Inpatient	Weekly for first 6 months	Twice a month for the first 6 months	Monthly	Final Visit (within 1 month after treatment)
Signed informed consent/assent	X					
History	X			X	X	X
Physical Exam	X	X		X	X	X
Blood specimen (4.4 mcl using microtainers) [#]	X	X		X	X	X
Urine pregnancy test*	X				X	X
Phone calls (clinical status and concomitant medication collection)			X		X **	

At baseline and then monthly for PT/PTT. At baseline and then weekly for other laboratory studies (see Section IX, E).

* For females of child-bearing potential.

** Phone calls will take place monthly (between the monthly visits)

G. Data Collection

Demographic and clinical information will be collected whenever clinical data are available via uniform baseline and follow up clinical data extraction forms to ensure accuracy and consistency. The essential demographic information includes age at diagnosis, gender, race and ethnicity, birth history, past medical history, and family history. The clinical information includes presence or absence of jaundice, hepatosplenomegaly, or ascites.

H. Compensation

Participants will not be compensated for study participation. Subjects will receive study medication, clinical supplies, and laboratory evaluations that are obtained outside the standard of care free of charge.

I. Withdrawal

Protocol – Compassionate Use of a Fish Oil-derived Intravenous Fat Emulsion (Omegaven[®]) to Reverse Parenteral Nutrition (PN) Induced Cholestasis

Data collected from patients who withdraw from the study will be included in the final analysis using intent to treat. Patient enrollment will continue until all 25 patients complete all requested study requirements outlined. It will be recommended that patients withdrawn from the protocol resume a reduced lipid intake, treat infections promptly as they occur and advance feedings as quickly as tolerated.

X. Assessment of Efficacy

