The primary endpoint will be reduction in conjugated or direct bilirubin level to below 1 mg/dl. Data from previous retrospective analyses and prospective uncontrolled studies suggest that from the inception of Omegaven® therapy, conjugated or direct bilirubin will remain elevated for approximately 8 weeks at levels comparable to those observed prior to administration of Omegaven®. Subsequently, levels are expected to fall by approximately 1 mg/dl/week until they normalize. The time to normalization will vary according to each patient's baseline conjugated or direct bilirubin level. Thus, a patient who begins Omegaven® with a conjugated or direct bilirubin level of 7 mg/dl is likely to experience normalization within 14 weeks (8+6 weeks). We will compare the group receiving Omegaven® with historical controls from our internal registry who have demonstrated cholestasis while on Intralipid®. We will compare changes in conjugated/direct bilirubin concentration over time between groups via Kaplan-Meier analysis (see Statistics section XIII).

Secondary endpoints will be: normalization of total bilirubin and liver enzymes. Differences in these values at the end of 14 weeks of therapy will be compared with those of controls via Kaplan-Meier analysis identical to that employed for conjugated and direct bilirubin levels. Furthermore, we expect that elevated triglyceride levels which might be present at the initiation of therapy will have normalized at the same time that liver profiles have normalized.

XI. Assessment of Safety/Data Safety Monitoring Board

A DSMB will monitor the study for the occurrence of adverse events (both serious and otherwise). A significant increase in the rate of adverse events would be cause for concern for the safety of participants in the study. Information on adverse events will be presented in several ways: (1) listings of serious adverse events with accompanying narrative summary by the PI; (2) summaries of adverse events by body system and type of event. This information will be presented to the DSMB.

The DSMB will also monitor the efficacy and the conduct of the study. Interim monitoring reports for the DSMB will include, but will not be limited to, such tabulations as:

1. platelet counts
2. essential fatty acid profiles
3. coagulation studies
4. liver profiles

5. renal profiles

The DSMB will meet at least once per year and possibly more frequently given the expected speed of recruitment and study medication administration.

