All adverse events will be followed until they are resolved or the patient's participation in the treatment ends (i.e., until a final report is completed for that patient).

In addition, all SAEs and those non serious events assessed by the Investigator as attributable (i.e. possibly, probably, definitely related to the drug) will continue to be followed even after the patient's participation in the treatment is over. Such events will be followed until they resolve or until the Investigator assesses them as "chronic" or "stable." Resolution of such events is to be documented in the CRF.

XIII. Statistics

We selected a study number of 25 patients (5 patients a year for 5 years) even though, statistically, a number of 19 will be satisfactory based upon power analysis. We know from our current registry that 10% of historic controls will experience resolution of cholestasis within 8 weeks while receiving Intralipid®, and we know from the data of Gura, et al (5) that approximately 50% of experimental subjects will experience resolution of cholestasis within eight weeks while receiving Omegaven®. Thus, achieving an alpha of 0.05 and a beta of 0.80, a sample size of 19 patients and 19 controls will be adequate (11). However, insofar as this is a compassionate release protocol, we will not refuse entry into the study even if we have shown statistically that Omegaven® is efficacious. We estimate that at most we will acquire five patients per year, and we anticipate that within five years, Omegaven® or SMOF (soy, MCT, olive oil and fish oil) parenteral lipids will have obtained FDA approval for clinical use.

The analysis populations will include (1) subjects receiving Omegaven® under this protocol and (2) historical controls from our internal registry who have demonstrated cholestasis while on Intralipid®. Paired t-tests will be used to report the statistical significance of differences between means. A p value of 0.05 or less will be considered significant. Wilcoxon Tests will be used to report the statistical significant differences between medians, and χ^2 tests/Fisher's exact tests will be used to report proportions. A Kaplan-Meier analysis will compare changes in conjugated/direct bilirubin concentration over time between groups. Cox proportional hazard models will be used to estimate crude and adjusted hazard ratios. Analyses will be performed via SAS 9.2 (SAS Institute Inc, Cary, NC) and S-Plus 8.1.1 (Insightful, Inc, Seattle, WA).

IX. Data Management

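### Enteral feeding, which the protocol names as a condition for PNAC to reverse on soy lipid, is not recorded or adjusted for, so a between-group difference in feeding would bias the Omegaven effect by an unknown amount

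*Combined protocol and SAP*

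**What the plan says.** **Narrative sections.** The opening summary reports unpublished experience that established PNAC without endotoxemia usually reverses, then qualifies it: "However, this may not be true if less than approximately 70% of daily calories are derived enterally". Section III says about a quarter of infants reverse even on soy lipid, "if those infants can experience small intestinal adaptation and ultimately tolerate and assimilate the majority of their calories via enteral nutrition". The summary describes the intended patients as those "who are unlikely to tolerate substantial enteral nutrition until several months following their small intestinal insult".

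**Operative sections.**
- IX.A: the nearest inclusion criterion is "Patients with intestinal failure on TPN". Criteria 3 and 4 require persistent cholestasis and failure of soy-lipid reduction. No inclusion or exclusion criterion concerns enteral intake or expected tolerance.
- IX.F and IX.G: neither the procedures, the procedures table nor the data list includes enteral intake. Section IX.G reads: "The clinical information includes presence or absence of jaundice, hepatosplenomegaly, or ascites".
- X: "The primary endpoint will be reduction in conjugated or direct bilirubin level to below 1 mg/dl". No feeding condition or time limit is attached.
- IV and IX.B (criterion 8): progress to enteral nutrition is a reason to end treatment. Under IX.I, data from withdrawn children are analysed by intent to treat.
- XIII: controls are registry children with cholestasis on Intralipid, with no stated matching or restriction on feeding. Adjusted hazard ratios are planned, but no covariate is named.

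**The concern.** The specific aim in Section II is causal: does replacing the lipid reverse PNAC? The protocol names a second route to the same endpoint, bowel adaptation, and treats it as important enough to define whom the study is for. Randomisation would balance that factor on average; a registry comparison does not. If prospectively followed children advance feeds faster or slower than the registry children did, the difference in bilirubin resolution mixes feeding with lipid. As written, the plan offers no means of seeing or correcting this. A covariate chosen after the results are known would carry little weight.

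Timing adds to the problem. Section X expects direct bilirubin to stay level for about 8 weeks and then fall by about 1 mg/dl per week. Many resolutions are therefore expected after two months or more, when adaptation also has had more time to occur.

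**Working it through.** **Step 1: the plan's own sample size.** Inputs from XIII: "10% of historic controls will experience resolution of cholestasis" within 8 weeks on Intralipid; about 50% on Omegaven; "achieving an alpha of 0.05 and a beta of 0.80", where 0.80 is read as power; 19 per group. Two-sided testing is assumed.

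Pooled formula, mean rate 0.30:

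n = [1.96·√(2·0.30·0.70) + 0.8416·√(0.10·0.90 + 0.50·0.50)]² / 0.40² = 19.4, so 20 per group.

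Arcsine formula:

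n = 2·[(1.96 + 0.8416) / (2·asin√0.50 − 2·asin√0.10)]² = 18.3, so 19 per group.

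The stated 19 reproduces. The sample-size arithmetic is not at fault.

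**Step 2: inert drug, more adaptation in the treated group.** Controls are held at the plan's 10%. The treated rate comes from feeding alone and is an assumption, except that 25% matches the quarter in Section III. Exact binomial enumeration, 25 per group: sum the probability of every pair of counts (a treated, b control) with a > b and two-sided p ≤ 0.05.

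| Treated rate from feeding alone | Falsely favours Omegaven, Fisher | Same, chi-square |
|---|---|---|
| 10% (no imbalance) | 0.4% | 2.4% |
| 15% | 2.8% | 7.9% |
| 20% | 8.5% | 17.2% |
| 25% | 18.0% | 30.0% |

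The nominal level in that direction is 2.5%.

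**Step 3: the opposite direction.** Suppose Omegaven gives 50%, but better feeding puts controls at 25% instead of 10%. By the normal approximation, power with 25 per group falls from 89.5% to 44.5%, and 58 per group would be needed for 80%. Imbalance can hide an effect as well as create one.

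**Step 4: single outcomes, two-sided Fisher.** 10/25 v 2/25 gives p = 0.018 and 9/25 v 2/25 gives p = 0.037. However, 8/25 v 2/25 gives p = 0.074, 6/25 v 2/25 gives p = 0.25 and 6/25 v 6/25 gives p = 1. One trial becomes significant through feeding alone only if the imbalance is large.

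**The case against.** Several stronger readings are tempting, and the documents do not support them.

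- **That resolution from adaptation is simply credited to Omegaven.** Registry children can adapt too, and their 10% may already include adapters. Only a difference between groups biases the comparison, and nothing shows its direction.
- **That about 6 of 25 treated children (25 × 0.25 = 6.25) would reach the endpoint on an inert drug.** The quarter describes infants with PNAC in general and has no time horizon. Entrants must have direct bilirubin of at least 3 mg/dl for more than 4 weeks and no fall after at least 30 days of lipid reduction, which plausibly selects against spontaneous resolution.
- **That feeding alone would readily give a significant result.** The significant examples in Step 4 need 36% to 40% against 8%, a gap with no basis in the text.
- **That the omission cannot be repaired.** Section IX.F allows clinical records to be used for research, the IX.G list need not be exhaustive, and withdrawals are listed for the DSMB. Feeding data may be recoverable.

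Two further limits apply. Resolution after weaning is bounded, because treatment ends and the final visit follows within a month. The text under the Data Management heading was not available to this review and might list further items.

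These arguments reduce the claimed size. They do not remove the point: a factor the protocol itself treats as prognostic is not assigned to data collection or adjustment in a non-randomised comparison. The stopping criterion does not help, because no rule says whether resolution at or after adaptation counts as an event, is censored or competes.

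**Conclusion.** The concern holds in a limited form. On the available text, the plan leaves its historical comparison open to confounding by enteral progress, with no specified way to measure or adjust for it. Direction and size are unknown. The 18% by Fisher's test (30% by chi-square) is an illustration that rests on an inert drug, 25 per group, and rates of 25% and 10% that differ only through feeding. Those two rates do not share a time horizon: the 10% is at 8 weeks and the quarter is untimed. They should not be read as an expected imbalance, nor as contradicting each other. A reader might infer that a positive result would be spurious. The documents support only that feeding could not be ruled out as a contributor, to a positive or a negative result.

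**What to change.** 1. **IX.G:** add percent of calories given enterally, and TPN status, to the baseline and follow-up extraction forms. Extract the same items for the registry controls from a comparable index date, defined before outcomes are examined.
2. **XIII:** name baseline percent enteral calories as a covariate in the Cox model already planned.
3. **X and XIII:** leave the primary result unchanged. Beside it, report a prespecified sensitivity analysis of time to direct bilirubin below 1 mg/dl reached before enteral calories pass the protocol's own approximate 70% figure, with passing it as a competing event. State that later enteral intake may itself be affected by treatment. For that reason this analysis should not replace the primary one, and a time-varying enteral covariate could adjust away part of a real effect.
4. **Summary and IX.A:** reconcile the narrative target population with the numbered criteria. Whether to restrict entry, and at what level, is a clinical and access question for the investigators of a compassionate-use protocol. No threshold is proposed here.

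**Cost:** two fields on an existing form, chart extraction for controls (possibly incomplete in older records), and one further analysis. That analysis will have fewer qualifying events and be less precise, and the 70% figure is approximate and rests on unpublished data. Adding a covariate also uses some of the limited information in about 25 treated children.
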